7.0 REGULATORY AND REPORTING REQUIREMENTS

The entities providing oversight of safety and compliance with the protocol require reporting as outline below.

The Washington University Human Research Protection Office (HRPO) requires that all events meeting the definition of unanticipated problem or serious noncompliance be reported as outlined in Section 7.2.

Novartis Pharmaceuticals requires that every SAE regardless of suspected causality that occurs after the patient has provided consent and after protocol-specified procedures have begun be reported as outlined in Section 7.4.

7.1 Definitions

7.1.1 Adverse Events (AEs)

Definition: any unfavorable medical occurrence in a human subject including any abnormal sign, symptom, or disease.

Grading: the descriptions and grading scales found in the revised NCI Common Terminology Criteria for Adverse Events (CTCAE) version 4.0 will be utilized for all toxicity reporting. A copy of the CTCAE version 4.0 can be downloaded from the CTEP website.

Attribution (relatedness), Expectedness, and Seriousness: the definitions for the

terms listed that should be used are those provided by the Department of Health and Human Services' Office for Human Research Protections (OHRP). A copy of this guidance can be found on OHRP's website: <http://www.hhs.gov/ohrp/policy/advevntguid.html>

7.1.2 Serious Adverse Event (SAE)

Definition: any adverse drug experience occurring at any dose that results in any of the following outcomes:

- Death
- A life-threatening adverse drug experience
- Inpatient hospitalization or prolongation of existing hospitalization
- A persistent or significant disability/incapacity (i.e., a substantial disruption of a person's ability to conduct normal life functions)
- A congenital anomaly/birth defect
- Any other experience which, based upon appropriate medical judgment, may jeopardize the subject and may require medical or surgical intervention to prevent one of the outcomes listed above

7.1.3 Unexpected Adverse Experience

Definition: any adverse drug experience, the specificity or severity of which is not consistent with the current investigator brochure (or risk information, if an IB is not required or available).

7.1.4 Life-Threatening Adverse Experience

Definition: any adverse drug experience that places the subject (in the view of the investigator) at immediate risk of death from the reaction as it occurred, i.e., it does not include a reaction that, had it occurred in a more severe form, might have caused death.

7.1.5 Unanticipated Problems

Definition:

- unexpected (in terms of nature, severity, or frequency) given (a) the research procedures that are described in the protocol-related documents, such as the IRB-approved research protocol and informed consent document; and (b) the characteristics of the subject population being studied;
- related or possibly related to participation in the research ("possibly related" means there is a reasonable possibility that the incident, experience, or outcome may have been caused by the procedures involved in the research); and
- suggests that the research places subjects or others at a greater risk of harm (including physical, psychological, economic, or social harm) than was

previously known or recognized.

7.1.6 Noncompliance

Definition: failure to follow any applicable regulation or institutional policies that govern human subjects research or failure to follow the determinations of the IRB. Noncompliance may occur due to lack of knowledge or due to deliberate choice to ignore regulations, institutional policies, or determinations of the IRB.

7.1.7 Serious Noncompliance

Definition: noncompliance that materially increases risks, that results in substantial harm to subjects or others, or that materially compromises the rights or welfare of participants.

7.1.8 Protocol Exceptions

Definition: A planned deviation from the approved protocol that are under the research team's control. Exceptions apply only to a single participant or a singular situation.

Pre-approval of all protocol exceptions must be obtained prior to the event.

7.2 Reporting to the Human Research Protection Office (HRPO) at Washington University

The PI is required to promptly notify the IRB of the following events:

- Any unanticipated problems involving risks to participants or others which occur at WU, any BJH or SLCH institution, or that impacts participants or the conduct of the study.
- Noncompliance with federal regulations or the requirements or determinations of the IRB.
- Receipt of new information that may impact the willingness of participants to participate or continue participation in the research study.

These events must be reported to the IRB within **10 working days** of the occurrence of the event or notification to the PI of the event. The death of a research participant that qualifies as a reportable event should be reported within **1 working day** of the occurrence of the event or notification to the PI of the event.

7.3 Reporting to the Quality Assurance and Safety Monitoring Committee (QASMC) at Washington University

The PI is required to notify the QASMC of any unanticipated problem occurring at WU or any BJH or SLCH institution that has been reported to and acknowledged by HRPO as

reportable. (Unanticipated problems reported to HRPO and withdrawn during the review process need not be reported to QASMC.)

QASMC must be notified within **10 days** of receipt of IRB acknowledgment via email to a QASMC auditor.

7.4 Reporting to Novartis

To ensure patient safety, every SAE, regardless of suspected causality, occurring

- after the patient has provided informed consent and until at least 30 days after the patient has stopped study treatment/participation
 - after protocol-specified procedures begin (e.g., placebo run-in, washout period, double-blind treatment, etc.) and 30 days after the patient has stopped study treatment
 - after the start of any period in which the study protocol interferes with the standard medical treatment given to a patient (e.g., treatment withdrawal during washout period, change in treatment to a fixed dose of concomitant medication) and until 30 days after the patient has stopped study treatment
- must be reported to Novartis within 24 hours of learning of its occurrence (**[contact]**). This includes serious, related, not related, labeled (expected) and unlabeled (unexpected) adverse experiences. All deaths during treatment or within 30 days following completion of active protocol therapy must be reported within 24 hours.

Any SAEs experienced after this 30 days period should only be reported to Novartis if the investigator suspects a causal relationship to the study drug. Recurrent episodes, complications, or progression of the initial SAE must be reported as follow-up to the original episode within 24 hours of the investigator receiving the follow-up information. A SAE occurring at a different time interval or otherwise considered completely unrelated to a previously reported one should be reported separately as a new event. The end date of the first event must be provided.

The original copy of the SAE Report and the fax confirmation sheet must be kept within the Trial Master File at the study site.

Follow-up information is sent to the same fax number as the original SAE Report Form was sent, using a new fax cover sheet, stating that this is a follow-up to the previously reported SAE, and giving the date of the original report. Each re-occurrence, complication, or progression of the original event should be reported as a follow-up to that event regardless of when it occurs. The follow-up information should describe whether the event has resolved or continues, if and how it was treated, whether the blind was broken or not (if applicable), and whether the patient continued or withdrew from study participation.

If the SAE is not previously documented in the Everolimus Investigator Brochure or Package Insert (new occurrence) and is thought to be related to the Novartis study drug, a DS&E associate may urgently require further information from the investigator for Health

[REDACTED]

8.1.4 Supplier(s)

Everolimus will be provided by Novartis Pharmaceuticals.

8.1.5 Dosage Form and Preparation

Everolimus is formulated as tablets for oral administration of 2.5 mg, 5 mg, and 10 mg strength. Tablets are blister-packed under aluminum foil, which should be opened only at the time of administration as the drug is both hygroscopic and light-sensitive.

8.1.6 Storage and Stability

Store at 25°C (77°F); excursions permitted between 15°C-30°C (59°-85°F). Store in the original container. Protect from light and moisture.

8.1.7 Administration

Everolimus is an oral drug which will be administered on an outpatient basis at a dose of 10 mg daily.

8.1.8 Special Handling Instructions

The extent of absorption of everolimus through topical exposure is not known. Therefore, caregivers are advised to avoid contact with suspensions of tablets. Wash hands thoroughly before and after preparation of either suspension.

9.0 CORRELATIVE STUDIES

9.1 Archived Tumor Tissue

If mutational testing has not already been performed, next generation sequencing and screening for mutations in TSC1, TSC2, NF1, NF2 and STK11 will be performed on archived formalin-fixed paraffin-embedded (FFPE) tumor tissue as part of the patient's routine care at any qualifying CLIA-certified laboratory that reports clinical next-generation sequencing of these genes. If the archival tissue does not have adequate viable cells for next generation sequencing to be performed, a fresh biopsy may be done prior to initiation of treatment. This is being done as part of routine care, and only patients who show a mutation in TSC1, TSC2, NF1, NF2 and STK11 may enroll to the study.

9.2 Fresh Tumor Biopsy

9.2.1 Collection of Specimen(s)

Accessible lesions that clearly show progression will be biopsied using standard of care parameters at the time of progression.

9.2.2 Handling of Specimen(s)

Collect and place in normal saline for delivery to the Siteman Cancer Center Tissue Procurement Core.

10.0 STUDY CALENDAR

Baseline evaluations are to be conducted within 14 days prior to start of protocol therapy. Scans and x-rays must be done no more than 28 days prior to the start of the protocol therapy. All visits have a window of +/- 3 days.

	Screening	Day 1 of each cycle	End of every even-numbered cycle	End of treatment	Follow-up ⁴
Informed consent	X				
H&P, ECOG PS, weight	X			X	
CBC	X	X ⁶		X	
CMP	X	X ⁶		X	
Hepatitis B and C testing	X				
Lipid panel ⁵	X				
INR	X				
HbA1c	X				
Pregnancy test ¹	X				
Standard of care imaging	X		X	X	
Archival tissue for TSC1, TSC2, NF1, NF2 and STK11 mutations ⁷	X				
Fresh tissue for research purposes				X ³	
Everolimus		X	----- X ²		
Adverse event assessment	X	-----	-----	-----	X
Concomitant medications	X	-----	-----	X	

1. Women of childbearing potential only
2. To be taken PO QD
3. At time of progression, biopsy of accessible lesions showing progression will be done
4. 30 days post-EOT
5. Should be performed periodically during treatment at the discretion of the treating physician
6. If screening labs are performed within 3 days prior to C1D1, the labs do not need to be repeated
7. Mutation testing can be done at any point prior to study enrollment

11.0 DATA SUBMISSION SCHEDULE

Case report forms with appropriate source documentation will be completed according to the schedule listed in this section.

Case Report Form	Submission Schedule
Original Consent Form	Prior to registration
On-Study Form Tumor Biopsy Form	Prior to starting treatment
Treatment Form	Every cycle
Toxicity Form Concomitant Medications Form	Continuous
Treatment Summary Form Tumor Biopsy Form	Completion of treatment
Follow Up Form	30 days after end of treatment
Tumor Measurement Form	Baseline, end of every even numbered cycles, and end of treatment
Adverse Events Form	See Section 7.0 for reporting requirements

12.0 MEASUREMENT OF EFFECT

12.1 Antitumor Effect – Solid Tumors

For the purposes of this study, patients should be re-evaluated for response every 8 weeks. In addition to a baseline scan, confirmatory scans should also be obtained 8 weeks (not less than 4) weeks following initial documentation of objective response.

Response and progression will be evaluated in this study using the new international criteria proposed by the revised Response Evaluation Criteria in Solid Tumors (RECIST) guideline (version 1.1) [Eur J Ca 45:228-247, 2009]. Changes in the largest diameter (unidimensional measurement) of the tumor lesions and the shortest diameter in the case of malignant lymph nodes are used in the RECIST criteria.

12.2 Disease Parameters

Measurable disease: Measurable lesions are defined as those that can be accurately measured in at least one dimension (longest diameter to be recorded) as >20 mm by chest x-ray, as >10 mm with CT scan, or >10 mm with calipers by clinical exam. All tumor measurements must be recorded in millimeters (or decimal fractions of centimeters).

Malignant lymph nodes: To be considered pathologically enlarged and measurable, a lymph node must be >15 mm in short axis when assessed by CT scan (CT scan slice thickness recommended to be no greater than 5 mm). At baseline and in follow-up, only the short axis will be measured and followed.

Non-measurable disease: All other lesions (or sites of disease), including small lesions (longest diameter <10 mm or pathological lymph nodes with ≥ 10 to <15 mm short axis), are considered non-measurable disease. Bone lesions, leptomeningeal disease, ascites, pleural/pericardial effusions, lymphangitis cutis/pulmonitis, inflammatory breast disease, and abdominal masses (not followed by CT or MRI), are considered as non-measurable.

Note: Cystic lesions that meet the criteria for radiographically defined simple cysts should not be considered as malignant lesions (neither measurable nor non-measurable) since they are, by definition, simple cysts.

‘Cystic lesions’ thought to represent cystic metastases can be considered as measurable lesions, if they meet the definition of measurability described above. However, if non-cystic lesions are present in the same patient, these are preferred for selection as target lesions.

Target lesions: All measurable lesions up to a maximum of 2 lesions per organ and 5 lesions in total, representative of all involved organs, should be identified as target lesions and recorded and measured at baseline. Target lesions should be selected on the basis of their size (lesions with the longest diameter), be representative of all involved organs, but in addition should be those that lend themselves to reproducible repeated measurements. It may be the case that, on occasion, the largest lesion does not lend itself to reproducible measurement in which circumstance the next largest lesion which can be measured reproducibly should be selected. A sum of the diameters (longest for non-nodal lesions, short axis for nodal lesions) for all target lesions will be calculated and reported as the baseline sum diameters. If lymph nodes are to be included in the sum, then only the short axis is added into the sum. The baseline sum diameters will be used as reference to further characterize any objective tumor regression in the measurable dimension of the disease.

Non-target lesions: All other lesions (or sites of disease) including any measurable lesions over and above the 5 target lesions should be identified as non-target lesions and should also be recorded at baseline. Measurements of these lesions are not required, but the presence, absence, or in rare cases unequivocal progression of each should be noted throughout follow-up.

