3.0 PATIENT SELECTION

3.1 Inclusion Criteria

1. Histologically confirmed diagnosis of advanced (metastatic, recurrent, or unresectable) cancer with mutations in any of the following genes: TSC1, TSC2, NF1, NF2 or STK11
2. Must have failed at least 1 standard of care systemic therapy for their malignancy.
3. Measurable disease defined as lesions that can be accurately measured in at least one dimension (longest diameter to be recorded) as ≥ 10 mm with CT scan, as ≥ 20 mm by chest x-ray, or ≥ 10 mm with calipers by clinical exam.
4. Prior therapy (chemotherapy, radiation therapy, and surgery) is allowed if completed at least 2 weeks prior to registration and if all treatment-related toxicities are resolved to \leq CTCAE grade 1, with the exception of alopecia and hematologic values otherwise meeting the bone marrow function criteria specified below.
5. At least 18 years of age.
6. ECOG performance status ≤ 2 (see Appendix A).
7. Normal bone marrow and organ function as defined below:
 - a. Leukocytes $> 3,000/\text{mcL}$
 - b. Absolute neutrophil count $> 1,500/\text{mcL}$
 - c. Platelets $> 100,000/\text{mcL}$
 - d. Hemoglobin > 9.0 g/dL
 - e. Total serum bilirubin ≤ 2.0 x IULN
 - f. AST(SGOT)/ALT(SGPT) ≤ 2.5 x IULN (≤ 5.0 x IULN in patients with liver metastases)

- g. Serum creatinine $\leq 1.5 \times$ IULN OR creatinine clearance > 45 mL/min/1.73 m² for patients with creatinine levels above institutional normal
 - h. Fasting cholesterol ≤ 300 mg/dL OR ≤ 7.75 mmol/L AND fasting triglycerides $\leq 2.5 \times$ IULN. NOTE: In case one or both of these thresholds are exceeded, the patient can only be included after initiation of appropriate lipid lowering medication
8. Able to swallow tablets.
 9. Women of childbearing potential, defined as all women physiologically capable of becoming pregnant, must use highly effective methods of contraception (please refer to Section 5.4) during the study and for 8 weeks after. Women are considered post-menopausal and not of childbearing potential if they have had 12 months of natural (spontaneous) amenorrhea with an appropriate clinical profile (e.g., age appropriate, history of vasomotor symptoms) or have had surgical bilateral oophorectomy (with or without hysterectomy) or tubal ligation at least six weeks prior to randomization. In the case of oophorectomy alone, only when the reproductive status of the woman has been confirmed by follow-up hormone level assessment is she considered not of childbearing potential.

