14.2 Data Analysis

The primary endpoint will be to describe the response rate using RECIST 1.1. Response rate will be defined as complete response (disappearance of all target lesion) plus partial response (a least a 30% decrease in the sum of diameters of target lesions). Secondary endpoint will be to further evaluate molecular markers of response or resistance using exome sequencing and transcriptome sequencing when feasible.

Demographic and clinical characteristics of the sample, as well as response, and toxicity by grade will be summarized using descriptive statistics. The overall response rate and its 90% confidence interval will be estimated. If possible, permutation tests will also be performed to compare the differences of secondary endpoints between responders and non-responders. The distribution associated with no difference (the null distribution) can be identified using the data in hand. If there is no difference between the values seen in responders and those in non-responders, then, for this purpose, it does not matter whether a given patient is labeled as a responder or a nonresponder. So we can randomly shuffle the response labels and calculate the test statistic from the shuffled data. If this procedure is repeated 10,000 times, the resulting 10,000 test statistics provide an accurate representation of the null distribution. The observed test statistic, based on patients assigned to the correct response group, is then compared to the null distribution. If the observed test statistic is unusually large or small, so very few values from the null distribution are larger or smaller than the observed test statistic, then the observed difference between responders and non-responders is unlikely if the null hypothesis were correct. In that case, we can reject the null hypothesis of no difference and conclude that there is a true difference between responders and non-responders. Then the null distribution

of the test statistics will be generated by simulating 10,000 datasets where the status of response was randomly shuffled. In order to quantify the extent to which the observed test statistic is “unusual,” a permutation test generates a p-value, which is equal to the proportion of test statistics from the label-shuffled samples that exceed the observed test statistics.

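### Inclusion 3 has no nodal short-axis rule, so a patient whose only disease is small CT-assessed nodes can enroll with no target lesion and cannot be scored as a partial response

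*Combined protocol and SAP*

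**What the plan says.** **Eligibility.** Section 3.1, item 3, carries its own definition: "Measurable disease defined as lesions that can be accurately measured in at least one dimension (longest diameter to be recorded) as" at least 10 mm on CT, at least 20 mm on chest x-ray, or at least 10 mm by calipers. It does not mention lymph nodes or the short axis, and it does not refer to Section 12.

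**Measurability for response.** Section 12.2 repeats the general rule with strict signs: "as >20 mm by chest x-ray, as >10 mm with CT scan, or >10 mm with calipers by clinical exam". It then adds a rule for nodes: "a lymph node must be >15 mm in short axis when assessed by CT scan". All remaining lesions, with nodes of 10 to below 15 mm short axis given as an example, "are considered non-measurable disease". Section 12.3 separately accepts superficial lesions of at least 10 mm by calipers and names palpable nodes among them.

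**Target lesions.** Section 12.2 draws these from measurable lesions only: "All measurable lesions up to a maximum of 2 lesions per organ and 5 lesions in total". For nodes, "If lymph nodes are to be included in the sum, then only the short axis is added into the sum".

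**Endpoint.** Section 14.2 counts complete plus partial responses. It words the first as disappearance of the target lesions and the second as a 30% or greater "decrease in the sum of diameters of target lesions". Section 14.1 enrolls 12 patients and declares preliminary efficacy if at least 2 of those 12 respond.

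**The concern.** Eligibility and the primary endpoint rest on two different definitions of measurable disease. The eligibility definition is the looser one for nodes seen on CT. A patient can pass the first and fail the second, and then has nothing on which a partial response can be measured. Section 14 has no evaluability or replacement rule, so such a patient stays in the denominator of 12. The error runs in one direction, against the drug. In a trial of 12 decided on two responders, a place given to a patient who cannot have a partial response is a noticeable loss.

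**Working it through.** **1. Does the gap exist?** Take a patient whose only disease is one CT-assessed node, 20 mm in longest diameter and 12 mm in short axis.

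- Inclusion 3: 20 mm is at least 10 mm, so the criterion is met.
- Section 12.2, nodal rule: 12 mm is not above 15 mm, so the node is not measurable.
- Section 12.2, target lesions: these come only from measurable lesions, so there is no target.
- Section 12.4.1: a partial response is defined on the target-lesion sum, so none can be scored.
- Section 12.4.3: the table for patients with non-measurable disease has no row that yields a partial response.
- Section 14.1: the patient counts as one of the 12.

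The result does not depend on whether the nodal cut-off means above 15 mm or at least 15 mm, since 12 mm fails both.

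**2. The plan's own design figure.** Inputs from Section 14.1: N = 12, success at 2 or more responders, null rate below 1% (0.01 used), alternative 30%, one-sided 0.05, 85% power. For n patients able to respond at rate p,

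P(X ≥ 2) = 1 − (1−p)^n − n·p·(1−p)^(n−1).

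- p = 0.01, n = 12: 1 − 0.8864 − 0.1074 = 0.0062 (attained one-sided level).
- p = 0.30, n = 12: 1 − 0.0138 − 0.0712 = 0.915 (attained power).

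N = 12 therefore satisfies the stated limits. The smallest n that does so with the two-responder rule is 10 (level 0.0043, power 0.851), so the design has two patients of slack over the stated 85%.

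**3. Effect of affected patients.** Let k of the 12 have no target lesion. The documents give no value for k, so the range below is an assumption. It is also assumed that none of the k is scored as a complete response. Power is the formula above with n = 12 − k and p = 0.30. The expected observed response rate is 30% × (12 − k)/12.

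| k (assumed) | Able to respond | Power at 30% | Expected observed rate |
|---|---|---|---|
| 0 | 12 | 0.915 | 30.0% |
| 1 | 11 | 0.887 | 27.5% |
| 2 | 10 | 0.851 | 25.0% |
| 3 | 9 | 0.804 | 22.5% |
| 4 | 8 | 0.745 | 20.0% |

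Power first falls below 85% at k = 3.

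**4. The same effect as a proportion.** If each enrolled patient has probability q of being in this group (again an assumption), the effective rate is 0.30 × (1 − q) with n = 12. For q = 5%, 10% and 15% the rates are 0.285, 0.270 and 0.255, and power is about 90%, 88% and 85%.

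**The case against.** The strongest reply is that the protocol should be read as a whole. Inclusion 3 uses the same term and nearly the same general sentence as Section 12.2. The nodal rule there is the more specific one, and Section 12.1 adopts RECIST 1.1 with the shortest diameter for malignant nodes. Many sites would apply the nodal rule at screening anyway. This lowers the likely number of affected patients but does not close the gap. Section 12.1 invokes RECIST for response and progression, not for eligibility, and under Section 4.1 eligibility is confirmed with a checklist, for which inclusion 3 is the stated criterion.

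A reader might also infer more than the documents support:

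- *That every node-only patient is affected.* Nodes above 15 mm short axis on CT are measurable and can be targets, and Section 12.3 accepts palpable nodes of at least 10 mm by calipers. Only patients whose sole disease is smaller, CT-assessed nodes are affected.
- *That such patients can never respond.* The non-measurable table in Section 12.4.3 allows a complete response, although Section 14.2 words it on target lesions. The power figures assume that none occurs.
- *That a 10 mm lesion or a 15 mm node is left unclassified.* Section 12.2 makes non-measurable disease a residual class, and the sizes listed there are only examples. Nothing falls outside both classes.
- *That the strict signs in 12.2 are a proven second contradiction.* They disagree with inclusion 3 and sit oddly beside the examples of below 10 and below 15 mm, but an underlined sign may have been lost when the PDF was read. This needs a check against the source file.

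**Conclusion.** The concern holds for a defined group: patients whose only disease is CT-assessed nodes with longest diameter at least 10 mm and short axis not above 15 mm. As written, they are eligible and counted but have no target lesion and no route to a partial response, so the response rate is biased downward. The size depends on a number that the documents do not give. With one or two such patients and no complete response among them, power stays at or above the stated 85% (88.7% and 85.1%); with three it is 80.4%. A reader might conclude that the trial is underpowered, but the documents do not support that: attained power with 12 patients able to respond is 91.5%, and nothing indicates that three or more would be affected. The correction is worth making because it is cheap and the error runs only one way.

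**What to change.** Reword inclusion 3 to require at least one measurable lesion, eligible as a target, as defined in Sections 12.2 and 12.3. State that this includes the short-axis rule for nodes assessed by CT and the caliper rule for palpable nodes, and carry the same wording into the eligibility checklist.

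Check in the source file whether the 10, 15 and 20 mm cut-offs in Section 12.2 are meant as at least rather than more than. Then make the 10 and 20 mm limits agree with inclusion 3, and the 10 and 15 mm limits agree with Section 12.2's own examples of non-measurable lesions. A sentence in Section 14.2 on how a patient found to have no target lesion counts in the primary analysis would cover enrollment errors.

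The cost is wording in two or three sections. The downside is that a few patients with only small CT-assessed nodes become ineligible.
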